#### **7.4.10 Anti-Myeloma Therapy**

The concurrent use of any approved or investigative drug with known or suspected anti-myeloma effect outside the scope of this trial is prohibited, with exception to those specifically permitted in section 7.4.

#### **7.4.11 Investigational Agents**

Other investigative agents (e.g., antibiotics or antiemetics) should not be used during the study.

### **8.0 DURATION OF THERAPY**

#### **8.1 Criteria for Removal from Study**

Treatment may continue until disease progression or clinical relapse, as defined in Sections 9.8 and 9.9 respectively, or until one or more of the following criterion applies:

- Participant withdraws consent
- Holding study drug(s) > 2 continuous weeks for adverse event(s)
- Adverse event(s) that, in the judgment of the Investigator, may cause severe or permanent harm or which rule out continuation of study drug.
- General or specific changes in the participant's condition render the participant unacceptable for further treatment in the judgment of the investigator
- Suspected or confirmed pregnancy
- Major violation of the study protocol
- Participant lost to follow-up
- The PI decides to remove the participant from study for any reason
- Death
- The treating center decides to close the study

#### **8.2 Duration of Follow-Up**

Participants will be followed for 18 months after removal from study or until death, whichever occurs first. Participants removed from study for unacceptable adverse events will be followed until resolution or stabilization of the adverse event, even if the follow-up exceeds 18 months.

### **9.0 CRITERIA FOR RESPONSE**

#### **9.1 Complete Response**

Complete response (CR) requires all of the following:

- Disappearance monoclonal protein by both protein electrophoresis and immunofixation studies from the blood and urine on at least two determinations, performed a minimum of six weeks apart
- <5% plasma cells in the bone marrow

- Disappearance of soft tissue plasmacytomas for at least six weeks

## 9.2 Stringent Complete Response

Stringent complete response (sCR) requires all of the following:

- CR as defined above
- Normal free light chain ratio
- Absence of clonal cells in the bone marrow by immunohistochemistry or immunofluorescence

## 9.3 Near-Complete Response

Near-complete response (nCR) requires all of the following:

- The presence of a residual monoclonal protein that is visible only on immunofixation studies, and not on serum or urine protein electrophoresis
- All other criteria are met for complete response.

## 9.4 Very Good Partial Response

Very good partial response (VGPR) requires all of the following:

- Serum and urine monoclonal protein detectable by immunofixation but not on electrophoresis for at least two determinations, performed a minimum of six weeks apart
- OR
- $\geq 90\%$  reduction in serum monoclonal protein with urine monoclonal protein  $< 100$  mg per 24 hours for at least two determinations, performed a minimum of six weeks apart.
  - If present,  $\geq 50\%$  reduction in the size of soft tissue plasmacytomas (by clinical or radiographic examinations) for at least six weeks.

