## 3.0 PARTICIPANT SELECTION

### 3.1 Inclusion Criteria

A participant must meet all of the following criteria to be eligible for enrollment.

- 3.1.1** Histologically confirmed diagnosis of multiple myeloma with a measurable disease parameter at time of screening. A measurable disease parameter is defined as one or more of the following:
- Serum monoclonal protein  $\geq 0.5$  g/dl.
  - 24 hour urine monoclonal protein  $\geq 0.2$  g/24 hour
  - Serum free light chain ratio  $> 5x$  normal ratio with an absolute difference of 10mg/dl between the involved and uninvolved free light chain.
  - Soft tissue plasmacytoma  $\geq 2$  cm measurable by either physical examination and/or applicable radiographs (e.g. MRI, CT, etc).
  - Bone Marrow Plasma Cells  $\geq 30\%$ .
- 3.1.2** Documentation of at least one line of prior myeloma therapy now with relapsed or refractory disease requiring re-treatment.
- 3.1.3**  $\geq 18$  years of age at time of signing the informed consent.

*Note:* No dosing or adverse event data are currently available on the use of carfilzomib in combination with PLD in participants  $< 18$  years of age. Thus, children and adolescents are excluded from this study but will be eligible for future pediatric phase 2 combination trials.

- 3.1.4** Performance status of ECOG  $\leq 2$  or Karnofsky  $\geq 60$  % (see Appendix A and B).

*Note:* Participants with lower performance status based solely on bone pain secondary to multiple myeloma will be eligible.

- 3.1.5** Required Laboratory Values
- ALT (SGPT) and AST (SGOT)  $< 2.5$  x the upper limit of the institutional normal value (ULN).
  - Total bilirubin  $\leq 1.5$  x ULN.
  - ANC  $\geq 1,000$ .
  - Hemoglobin  $\geq 8$  g/dl.
  - Platelets  $\geq 50,000$ .
  - Creatinine clearance  $> 15$  ml/minute using Cockcroft-Gault formula (See Appendix C).
  - For those participants receiving warfarin (Coumadin), unfractionated heparin, or low-molecular weight heparin therapy, the applicable

coagulation parameter that is being monitored must be within the accepted therapeutic ranges for those indications.

*Note:* Transfusions and/or growth factor dependent participants are not excluded if the above parameters can be achieved with such support.

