## 9.5 Partial Response

Partial response (PR) requires all of the following:

- $\geq 50\%$  reduction in the level of the serum monoclonal protein for at least two determinations performed a minimum of six weeks apart.
- Reduction in urine monoclonal protein by either  $\geq 90\%$  or to  $\leq 200$  mg for at least two determinations performed a minimum of six weeks apart.
- If present,  $\geq 50\%$  reduction in the size of soft tissue plasmacytomas (by clinical or radiographic examinations) for at least six weeks.
- If serum and urine monoclonal protein are unmeasurable, a  $\geq 50\%$  decrease in difference between the involved and uninvolved free light chain levels is required in place of monoclonal protein criteria (The absolute decrease must

- be  $\geq 10$  mg/dl)
- If serum and urine monoclonal protein are unmeasurable and serum free light chain is unmeasurable, a  $\geq 50\%$  reduction in plasma cells is required in place of monoclonal protein provided that baseline bone marrow plasma cell percentage was  $\geq 30\%$

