### **15.0 ENDPOINTS**

#### **15.1 Primary Outcome Analyses**

The primary endpoint for each arm of the phase II portion of this trial is the proportion of confirmed tumor responses. A confirmed response is defined to be a CR, VGPR, or PR noted as the objective status. Response will be evaluated using up to 12 cycles of treatment. All participants meeting the eligibility criteria who have signed a consent form and have begun treatment will be evaluable for response.

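### The first VGPR alternative in section 9.4 asks for no change from baseline, so a narrow group of light-chain or marrow entrants could count as responders with unchanged disease

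*Combined protocol and SAP*

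**What the plan says.** **Entry (3.1.1).** "A measurable disease parameter is defined as one or more of the following". The list includes serum M-protein, urine M-protein, free light chains, soft tissue plasmacytoma and marrow plasma cells of at least 30%. The light-chain item is a ratio above five times normal "with an absolute difference of 10mg/dl between the involved and uninvolved free light chain". No item requires M-protein visible on electrophoresis if another item is met.

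**VGPR (9.4).** Two alternatives are joined by OR:
- First: "Serum and urine monoclonal protein detectable by immunofixation but not on electrophoresis for at least two determinations", at least six weeks apart.
- Second: a "reduction in serum monoclonal protein with urine monoclonal protein" condition, meaning a serum fall of at least 90% with urine below 100 mg per 24 hours, also seen twice six weeks apart.

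If plasmacytomas are present, there must also be a 50% or greater "reduction in the size of soft tissue plasmacytomas (by clinical or radiographic examinations) for at least six weeks".

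**PR (9.5).** When serum and urine M-protein are unmeasurable, a fall of at least 50% in the difference between involved and uninvolved "free light chain levels is required in place of monoclonal protein criteria". If light chains are also unmeasurable, the substitute is a fall of at least 50% in marrow plasma cells, provided the baseline was at least 30%.

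**Primary endpoint (15.1).** "A confirmed response is defined to be a CR, VGPR, or PR noted as the objective status". Section 5.3 counts the same three categories as successes.

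**The concern.** The second VGPR alternative measures a fall. The first describes only how the M-protein looks on study. For a participant whose M-protein was visible on electrophoresis at baseline, becoming electrophoresis-negative is itself a fall, so the wording works. For a participant whose protein was immunofixation-only at screening, the same finding can simply be the baseline state seen again.

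For that participant the response scale is inverted: the higher grade needs no fall and the lower grade needs at least 50%. Because VGPR is a success, unchanged disease would add to the count that decides whether the regimen is called active. It would also blur the correlative objective in section 1.7, which looks for tumour characteristics that predict at least VGPR.

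**Working it through.** **Step 1. Does any other rule block the result?** Take a participant who entered on light chains or marrow alone, has immunofixation-only protein in both serum and urine at screening, has no plasmacytoma, and whose disease does not change.

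| Rule | Does it stop VGPR? |
|---|---|
| 9.4, first alternative | No. It is met by two unchanged results six weeks apart. |
| 9.4, plasmacytoma condition | No. It applies only if plasmacytomas are present. |
| 9.5 substitutes | No. They sit under PR, and 9.4 does not require PR to be met. Contrast 9.2, where sCR explicitly requires CR. |
| 9.3, nCR | No. It uses the same immunofixation-only picture but adds the other CR criteria, including marrow plasma cells below 5%. Section 9.4 has no such addition. |
| 9.7, SD | No. SD is what remains when no other category is met. |
| 9.8, PD override | No. It removes progressors. A light-chain rise below 25%, or below 10 mg/dl in absolute terms, is not PD by that criterion. |
| 10.0, 24-hour urine to confirm VGPR | No. It adds a test, not a required fall. |

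Nothing in section 9 states generally that response requires change from baseline.

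**Step 2. The decision rules without any such participant.** The documents give two phase II rules: success at 6 or more of 17 (section 5.3) and at 8 or more of 24 (section 16). That conflict is a separate matter, so both are used. With X binomial and the section 16 null rate of 20%:
- P(X ≥ 6 | n = 17, 0.20) = 0.106
- P(X ≥ 8 | n = 24, 0.20) = 0.089, against the stated significance level of 0.10

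**Step 3. Worst case.** Let k participants be certain to score VGPR and let the others respond at 20%. The false-positive chance is P(X ≥ r − k | n − k, 0.20). The value of k is an assumption, since the documents give no frequency.

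| k | r = 6, n = 17 | r = 8, n = 24 |
|---|---|---|
| 0 | 0.106 | 0.089 |
| 1 | 0.202 | 0.160 |
| 2 | 0.352 | 0.267 |

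**Step 4. Allowing for progression.** Certainty is too strong, because a participant who meets PD is not a responder. For one participant with success probability q, the chance is q · P(X ≥ r − 1 | n − 1, 0.20) + (1 − q) · P(X ≥ r | n − 1, 0.20). With q = 0.65, an assumption:
- 17 participants: 0.65 × 0.2018 + 0.35 × 0.0817 = 0.160
- 24 participants: 0.65 × 0.1598 + 0.35 × 0.0715 = 0.129

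The same weighting with two such participants gives 0.231 and 0.180. The value 0.65 is close to the disease control reported in section 1.3.5.2 for single-agent carfilzomib (18% + 7% + 41% = 66% in one study, and about 65% as a later summary figure). Those patients were on an active drug, so it is an illustration and not an estimate for an inactive regimen.

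**The case against.** The strongest reply is that the affected group is small and may be empty. Read literally, the first alternative asks for immunofixation-only protein in serum and in urine. A participant with protein in one compartment, or with negative immunofixation in either, does not clearly qualify, and the text does not say how such cases score. The participant must also have no plasmacytoma and must stay free of PD over two assessments at least six weeks apart, although section 3.1.2 requires disease that needs re-treatment. All of this stands and sets the scope of the point.

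A reader might infer that every light-chain or marrow entrant is an automatic responder, that VGPR is generally easier to reach than PR, or that the trial's error rate is in fact doubled. The documents support none of these. The inversion affects only the group described. The PD override can still remove its members. The expected number is unknown, and if it is zero there is no inflation.

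It can also be said that an experienced assessor takes response to mean reduction and would not score unchanged disease as VGPR. That may be so in practice. But section 9 does not state it, and a primary endpoint with a fixed cut-off should not depend on an unwritten convention. This part of the reply does not remove the defect.

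**Conclusion.** The point holds in a limited form. As written, section 9.4 gives a wrong classification for a definable group: light-chain or marrow entrants with immunofixation-only protein in serum and urine at screening, no plasmacytoma and no PD. Their unchanged disease would count as a success.

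The figures of 0.202 and 0.352 (17 participants) and 0.160 and 0.267 (24 participants) are upper bounds for one and two such participants. They assume certain success in those participants and a 20% rate in everyone else. With an assumed 0.65 chance of success, one participant gives 0.160 or 0.129. All of these exceed the stated 0.10, so even a single case could matter in a trial this small. What cannot be claimed is that such a case will occur: the documents give no frequency.

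**What to change.** In section 9.4 and on the response form:
1. Limit the immunofixation-only alternative to participants whose M-protein was visible on serum or urine electrophoresis at baseline. The test should be visibility and not the section 3.1.1 thresholds. Otherwise someone whose visible but sub-threshold protein truly disappears from electrophoresis would lose the route.
2. For participants with no electrophoresis-visible M-protein at baseline who entered on light chains or marrow, judge response by the existing section 9.5 substitutes, with PR as the ceiling. This needs no new threshold. The documents state no light-chain criterion for VGPR, and the 90% in 9.4 applies to serum M-protein.
3. For plasmacytoma-only entrants, keep the existing plasmacytoma reduction of at least 50% as the required fall. The section 9.5 substitutes cover only light chains and marrow, so applying item 2 to these participants would leave them no route to response.

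**Cost.** A short wording change and a form edit. Serum free light chains are already scheduled on Day 1 of each cycle. Marrow-only entrants need a repeat marrow, but the 9.5 marrow substitute already implies one. The observed response rate, and the VGPR rate in these participants, may be slightly lower.

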## 9.5 Partial Response

Partial response (PR) requires all of the following:

- $\geq 50\%$  reduction in the level of the serum monoclonal protein for at least two determinations performed a minimum of six weeks apart.
- Reduction in urine monoclonal protein by either  $\geq 90\%$  or to  $\leq 200$  mg for at least two determinations performed a minimum of six weeks apart.
- If present,  $\geq 50\%$  reduction in the size of soft tissue plasmacytomas (by clinical or radiographic examinations) for at least six weeks.
- If serum and urine monoclonal protein are unmeasurable, a  $\geq 50\%$  decrease in difference between the involved and uninvolved free light chain levels is required in place of monoclonal protein criteria (The absolute decrease must

- be  $\geq 10$  mg/dl)
- If serum and urine monoclonal protein are unmeasurable and serum free light chain is unmeasurable, a  $\geq 50\%$  reduction in plasma cells is required in place of monoclonal protein provided that baseline bone marrow plasma cell percentage was  $\geq 30\%$

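### Read as written, section 9.5 gives no partial-response route to urine-only participants or to some plasmacytoma-only participants, yet section 15.1 keeps them in the denominator

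*Combined protocol and SAP*

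**What the plan says.** **Entry (3.1.1).** "A measurable disease parameter is defined as one or more of the following": serum protein of at least 0.5 g/dl; "24 hour urine monoclonal protein" of at least 0.2 g/24 h; an abnormal free light chain ratio with a sufficient absolute difference; a soft tissue plasmacytoma of at least 2 "cm measurable by either physical examination and/or applicable radiographs"; or marrow plasma cells of at least 30%.

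**PR (9.5).** All bullets must be met.
- Serum: a fall of at least 50%, stated as a "reduction in the level of the serum monoclonal protein for at least two determinations performed a minimum of six weeks apart", with no condition attached.
- Urine: "Reduction in urine monoclonal protein by either" at least 90% or to 200 mg or less.
- Plasmacytoma: at least 50% shrinkage for six weeks, required only if a lesion is present.
- Light-chain substitute, which opens "If serum and urine monoclonal protein are unmeasurable, a" and then asks for a fall of at least 50% in the difference between involved and uninvolved light chains.
- Marrow substitute, where light chains are unmeasurable as well: a 50% or greater "reduction in plasma cells is required in place of monoclonal protein provided that baseline bone marrow plasma cell percentage was" at least 30%.

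**Very good partial response (VGPR, 9.4).** One alternative is "Serum and urine monoclonal protein detectable by immunofixation but not on electrophoresis". The other is a serum fall of at least 90% with low urine protein.

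**Endpoint (15.1).** CR, VGPR and PR are successes, and every eligible, consented participant who has started treatment is evaluable.

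**The concern.** The entry rule and the response rule do not match. A participant can enter on a single parameter that 9.5 then gives no means of using to show a partial response. Section 9.8 needs only one criterion for progression, so the same participant can progress on that parameter.

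The phase 2 conclusion rests on one count of responders against a fixed cut-off, so one or two misclassified participants can change it. Duration of response in 15.2 is defined only for confirmed responders, so these participants would be lost there too. If assessors have to supply the missing condition themselves, primary-endpoint scoring becomes a matter of discretion.

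**Working it through.** **1. Each single-parameter entry route in 3.1.1 against the bullets of 9.5.**

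| Entered on | Serum bullet | Substitutes | PR route |
|---|---|---|---|
| Serum protein | can be met | not needed; urine bullet taken as met at 200 mg or less | yes |
| Light chains only | replaced | light-chain substitute applies | yes |
| Marrow at least 30% only | replaced | marrow substitute applies | yes |
| Urine only, no serum protein | nothing to fall | both need serum and urine unmeasurable; urine is measurable | none |
| Plasmacytoma only, light chains unmeasurable, marrow <30% | nothing to fall | light-chain fall cannot be shown; marrow barred by the 30% proviso; shrinkage is an added condition and replaces nothing | none |

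**2. VGPR for the last two rows.** With no serum protein, neither the immunofixation alternative (serum and urine protein both detectable) nor the 90% serum fall can be met.

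**3. What stays open.** A urine-only participant can reach CR, or near-complete response (9.3), if the plasmacytoma bullet in 9.1 is read as applying only where a lesion is present. Section 15.1 does not list near-complete response as a success, although 15.2 includes it for duration of response. A plasmacytoma-only participant can reach CR if protein that was never present is taken as having disappeared.

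**4. Worked case (assumed values).** A urine-only participant falls from 2,000 to 150 mg/24 h, confirmed: (2,000 − 150)/2,000 = 92.5%. PR fails on the serum bullet. Minimal response (9.6) has its own unqualified serum bullet, and the note there does not help because the serum requirement for minimal response is unmet too. Section 9.7 then makes this stable disease.

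**5. The plan's own figure.** Section 16 states alpha 0.10 and gives no numerical power. Sections 5.3 (17 participants, ineffective at 5 or fewer) and 16 (24 participants, ineffective at 7 or fewer) conflict, so both rules are shown. With null and target rates of 20% and 40%:
- 24 participants, 8 or more: P(Bin(24, 0.2) ≥ 8) = 0.089; P(Bin(24, 0.4) ≥ 8) = 0.808.
- 17 participants, 6 or more: P(Bin(17, 0.2) ≥ 6) = 0.106; P(Bin(17, 0.4) ≥ 6) = 0.736.

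The stated 0.10 holds as a nominal ceiling for the 24-participant rule and is slightly exceeded by the 17-participant rule.

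**6. Effect of k participants who cannot count.** The chance of declaring success is P(Bin(n − k, p) ≥ r). The documents do not give k; it is assumed.

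| k | Power, 6 of 17 | Power, 8 of 24 | Alpha, 6 of 17 | Alpha, 8 of 24 |
|---|---|---|---|---|
| 0 | 0.736 | 0.808 | 0.106 | 0.089 |
| 1 | 0.671 | 0.763 | 0.082 | 0.072 |
| 2 | 0.597 | 0.710 | 0.061 | 0.056 |

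These losses are upper bounds because CR is ignored. If each affected participant has an assumed 10% chance of CR, power is 0.687 or 0.774 for k = 1, and 0.633 or 0.736 for k = 2.

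**The case against.** The strongest reply is that this reads one bullet strictly and others loosely. Section 9.1 asks for plasmacytomas to disappear without saying 'if present', and 9.6 has a similar gap. The urine bullet in 9.5 speaks of a reduction even for someone with no urine protein. Read strictly throughout, much of the trial would be barred from response, which points to loose drafting and not to an intended exclusion. Study calendar footnote h supports this. Apart from screening and confirmation of CR or VGPR, it requires serial 24-hour urines only from participants with at least 0.2 g/24 h at screening. Urine is thus already followed by measurability at baseline. An assessor may well read 'if measurable' into the serum bullet, and no section describes a scoring algorithm that would prevent it.

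Most of this stands. It limits the point to what the text says and is no forecast of how responses will be scored. It does not remove the gap. Footnote h says nothing about the serum bullet, and 9.5 does attach 'if present' to plasmacytomas and provides substitutes for unmeasurable protein, so the missing condition cannot simply be assumed.

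A reader might infer that these participants are shut out of success altogether. The documents do not support that, since CR remains reachable on the readings above. Nor do they show that participants with detectable serum protein below 0.5 g/dl are locked out. Section 9.5 sets no minimum serum level and leaves 'unmeasurable' undefined, so those participants are ambiguous.

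**Conclusion.** The point holds as a defect in the wording of the primary-endpoint definition. On the text of 9.5, two groups that are eligible under 3.1.1 and evaluable under 15.1 have no PR route, and 9.4 does not rescue them. A real partial response can therefore be scored as a failure.

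The direction is conservative. Response rate, power and alpha all fall, so a reader who infers a risk of falsely declaring the regimen active would be mistaken. The illustrative size is a power loss of 0.736 − 0.671 = 0.065 (6 of 17) or 0.808 − 0.763 = 0.045 (8 of 24) for each trial with one affected participant. It rests on an assumed number affected, no CR in that participant, and a true 40% rate in the others. It is not an estimate of this trial's loss. The second group also needs several conditions together and may be small. The alphas of 0.106 and 0.089 are computed here; the only alpha the plan states is 0.10.

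A reader might also infer that urine-only participants need a new minimum percentage fall, because a baseline close to 200 mg/24 h needs little change to reach 200 mg or less. The documents already require a reduction and set that limit themselves. A stricter threshold for one subgroup would be a separate judgement and is not needed to repair the gap.

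**What to change.** Before responses are reviewed, amend 9.5 to:
- define unmeasurable as below the 3.1.1 threshold at baseline;
- apply the serum and urine bullets only to parameters measurable at baseline;
- where a plasmacytoma is the only measurable parameter, let the existing criterion of at least 50% shrinkage for six weeks stand in place of the monoclonal protein criteria.

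Carry the measurable-at-baseline qualifier into 9.4 and 9.6 for consistency.

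The cost is mostly wording. The thresholds are already in the protocol, and footnote h already schedules urine collection for those who need it. Palpable lesions can be followed at the physical examination (footnote e), which 9.5 accepts. The one practical cost is that plasmacytoma-only participants with non-palpable lesions need a repeat image to show six weeks, which footnotes k and m now provide for only when clinically indicated; the calendar should say so. The change removes the artificial loss of power and also raises alpha back to the k = 0 values, which is why it should be settled without sight of responses.

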## 10.0 STUDY CALENDAR

Assessment *	Screening a	Cycles 1 through 6						Cycles 7 and beyond				End of Study b	Follow-up c	
		D1	D2	D8	D9	D15	D16	D1	D8	D15	D22			
Sign informed consent	X													
Medical & treatment history	X													
Vital signs d	X	X	X	X	X	X	X	X	X	X	X	X		
Physical exam e	X	X 						X						
Toxicity assessment	X	X	X	X	X	X	X	X	X	X	X	X	X	
CBC w/ differential	X	X		X		X		X	X	X	X	X	X	
Chemistries f	X	X	X	X	X	X	X	X	X	X	X	X	X	
PT/INR & PTT	X	X 												
SPEP & IFIX g	X	X 				X 		X					X	
24-hour urine total protein, UPEP, & IFIX gh	X	X 				X 		X					X	
Serum free light chains	X	X 				X 		X					X	
Quantitative immunoglobulins (IgA, IgG, IgM)	X	X 				X 		X					X	
Beta-2 microglobulin	X	X 						X					X	
Serum $\beta$ HCG j	X	X						X					X	
EKG & Chest x-ray	X													
MUGA or Echo m	X													
Imaging for plasmacytoma assessment km	X												X 	
Skeletal survey m	X												X 	
Bone marrow biopsy & aspirate n	X												X 	
Correlative samples o	X												X 	
Carfilzomib administration		X	X	X	X	X	X	X	X	X	X	X		
PLD administration				X										
Dexamethasone administration p		X	X	X	X	X	X	X	X	X	X	X		
Follow-up for survival														X

\* All assessments allowed a window of +/- 2 days for scheduling issues (such as holidays)

a: Screening period is D-21 though D1 prior to Carfilzomib dose

b: End of study must be within 30 days of last dose of study drug

c: Follow-up takes place every 3 months for up to 18 months or until resolution or stabilization of adverse events, whichever is longer

d: To be done within 1 hour prior to carfilzomib administration.

e: Physical exam includes height, weight, BSA, performance status, neurological assessment and plasmacytoma assessment if indicated .

f: Chemistries include Complete Metabolic Panel with Renal and Hepatic Panels, LDH, Magnesium, Phosphorous, Uric Acid.

g: SPEP = serum protein electrophoresis, IFIX=immunofixation, UPEP= urine protein electrophoresis.

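### A response first seen shortly before treatment stops may have no planned visit late enough to confirm it six weeks later; the effect on the phase II decision is small, and so is the remedy

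*Combined protocol and SAP*

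**What the plan says.** Section 15.1 sets the endpoint: "The primary endpoint for each arm of the phase II portion of this trial is the proportion of confirmed tumor responses". Success is CR, VGPR or PR. Every eligible, consented participant who began treatment is evaluable, and response is assessed over up to 12 cycles.

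The confirmation interval is in Section 9. For PR, 9.5 asks for a 50% or greater "reduction in the level of the serum monoclonal protein for at least two determinations performed a minimum of six weeks apart". For VGPR, the 90% route in 9.4 requires urine M-protein below 100 "mg per 24 hours for at least two determinations, performed a minimum of six weeks apart". CR in 9.1 has the same interval. Soft-tissue plasmacytoma criteria, where they apply, must hold for six weeks. The free-light-chain and marrow plasma-cell routes to PR in 9.5 state no six-week repeat.

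The Section 10.0 calendar places M-protein tests at screening, Cycle 1 Day 15, Day 1 of each 28-day cycle and end of study. Footnote b reads "End of study must be within 30 days of last dose of study drug", and assessments have a window of two days either way. After that, "Follow-up takes place every 3 months for up to 18 months or until resolution or stabilization of adverse events, whichever is longer". Section 11.0 attaches only a Survival Form to follow-up; the last Disease Assessment and Response Assessment forms belong to the end-of-study visit.

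Section 9.7 makes stable disease the default when no other category is met. No rule covers a response that is seen once and cannot be repeated.

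**The concern.** The endpoint needs two values 42 days apart, but planned disease assessment ends at most 30 days after the last dose. A participant who first meets PR and then stops within days, without progressing, cannot be confirmed by any planned visit. The path is foreseeable: 8.1 removes a participant after a hold of more than two continuous weeks for adverse events. (Section 6.2.1 uses more than four weeks; the two passages need reconciling, which is a separate matter.)

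The phase II decision is a fixed count, at least 8 of 24 in Section 16.0 or at least 6 of 17 in Section 5.3, so each unconfirmable response moves the result towards calling the regimen ineffective. It does so because of the visit schedule, not because lack of response was observed.

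**Working it through.** **Timing.** Let d be the number of days from the first qualifying value to the last dose. The latest permitted end-of-study visit is d + 30 days after that value. Confirmation needs d + 30 ≥ 42, so d ≥ 12. If the two-day window also extends this visit, d + 32 ≥ 42 gives d ≥ 10.

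- d < 12, including negative d when dosing was already on hold: no planned visit can confirm.
- 12 ≤ d ≤ 41: confirmation depends on how late in its 30-day window the visit is booked.
- d ≥ 42: any end-of-study visit after the last dose is late enough.

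Examples, counting Cycle 1 Day 1 as day 1:

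| First qualifying value | Last dose | Latest visit | Gap in days |
|---|---|---|---|
| C1D15 (day 15) | C1D16 (day 16) | day 46 | 31 |
| C2D1 (day 29) | C2D8 (day 36) | day 66 | 37 |
| C2D1 (day 29) | C2D15 (day 43) | day 73 | 44 |
| C2D1 (day 29), already on hold | C1D16 (day 16) | day 46 | 17 |

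Only the third row can reach 42 days. The others fall short even with two days added. The C2D1 pattern repeats through Cycle 6. A response first seen at the end-of-study visit has no later planned value at all.

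**The plan's own figures.** Section 16.0 gives p0 = 0.20, p1 = 0.40 and a significance level of 0.10, with no power value. Exact binomial:

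- 24 participants, 8 or more: P(X ≥ 8 | 0.20) = 0.089; P(X ≥ 8 | 0.40) = 0.808.
- 17 participants, 6 or more: P(X ≥ 6 | 0.20) = 0.106; P(X ≥ 6 | 0.40) = 0.736.

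So 0.10 works as a nominal ceiling for the 24-participant rule. The two sample sizes conflict and must be reconciled separately; I carry both.

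**Share of responders affected.** The documents give no rate of stopping without progression, so I assume h = 0.02 to 0.06 per 28-day cycle, with u = 1 − exp(−h × days/28).

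- Strictly unconfirmable, 12 days: 1 − exp(−0.02 × 12/28) = 0.009; 1 − exp(−0.06 × 12/28) = 0.025.
- Upper bound, if every visit in the 12-to-41-day band is booked too early, 42 days: 1 − exp(−0.03) = 0.030; 1 − exp(−0.09) = 0.086.

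These shares leave out participants already on hold at the first qualifying value, for whom the documents give no basis.

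Expected strictly lost responses at 40%: from 17 × 0.40 × 0.0085 = 0.06 to 24 × 0.40 × 0.0254 = 0.24 in the whole trial.

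**Operating characteristics**, reading 20% and 40% as first-observed response rates and replacing p by p(1 − u) with the strict share:

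| Rule | Power, no loss | Power, u = 0.9% to 2.5% | Type I error, no loss | Type I error, u = 0.9% to 2.5% |
|---|---|---|---|---|
| 8 of 24 | 0.808 | 0.799 to 0.779 | 0.089 | 0.086 to 0.079 |
| 6 of 17 | 0.736 | 0.727 to 0.707 | 0.106 | 0.102 to 0.096 |

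The drop in power is the chance that the decision reverses: about 0.01 to 0.03 under either rule.

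**The case against.** The strongest objection is that 15.1 defines success as confirmed response. If the 20% and 40% in Section 16.0 are confirmed-response rates, exits before confirmation are already inside them, and stated power does not fall. The documents do not say otherwise. This stands, and the power figures above hold only under the other reading.

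Second, a six-week repeat with an all-treated denominator is a respectable conservative convention, and the phase II objective covers toxicity as well as efficacy. That also stands as a defence of the convention. It does not defend a calendar that rules out the repeat for some participants, and the change proposed here keeps the convention.

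Third, toxicity need not end assessment. PLD or dexamethasone can be stopped with the participant still on study (5.1, 6.2.1), and phase II dose changes and delays may depart from the tables at the PI's discretion. Sections 9.4 and 9.5 do not require the second value to be on treatment, and no passage forbids an extra draw. Calendar footnotes h and n foresee confirmatory urine and marrow tests for the deeper responses. These points narrow the problem, but none of them plans a serum value after the end-of-study visit, so confirmation would depend on local practice.

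A reader might infer that everyone who stops within six weeks of first response is lost, or that the primary estimate is materially biased. The documents support neither. Loss is forced only below 12 days or when dosing was already on hold. Above that it depends on booking, and the size rests on assumed rates. A reader might also dwell on the chance that the count lands exactly on the pass boundary at 40%, which is 0.136 for 8 of 24 and 0.184 for 6 of 17. That is not the chance of a reversed decision, because a response must also be lost.

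**Conclusion.** The point holds in a limited form. For CR, VGPR and M-protein PR, the schedule cannot deliver its own confirmation rule when the last dose falls fewer than 12 days after the first qualifying value (fewer than 10 if the window applies to that visit), or when dosing was already on hold and does not resume. That such a participant counts as a non-success is inferred from 9.7 and 15.1; no sentence says so. The free-light-chain and marrow routes to PR are not affected.

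At the assumed stopping rates, 0.9% to 2.5% of responders are strictly unconfirmable, with 3% to 9% as the upper bound. Under the first-observed reading of 40%, this costs about one to three percentage points of power, with a slight fall in type I error. The direction is towards declaring the regimen ineffective. The conclusion also rests on survival being the only efficacy item planned after end of study; adverse-event follow-up can continue, and the Section 11.0 forms support this reading. This is a small, cheaply closed gap and does not threaten the design.

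**What to change.** Amend footnote b, 8.2 and 15.1 together.

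- Footnote b and 8.2: when a participant stops treatment without progression while a response is unconfirmed, time the end-of-study visit within its existing 30-day window to fall at least six weeks after the first qualifying value, where possible. Otherwise take one M-protein draw (serum, and urine if it was measurable) at least six weeks after that value, at or before the first 3-month follow-up contact, and before any new anti-myeloma therapy.
- 15.1: state that this off-treatment value counts for confirmation, that the participant is a non-responder if it is not obtained, and that the number of responses confirmed this way is reported. Without this, the present limit to up to 12 cycles of treatment leaves the status of an off-treatment value open.

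The timing change costs nothing beyond scheduling. The extra draw is one routine sample in a few participants. The downside is that the confirming value is taken off treatment, which is why the count should be reported. Treatment rules, decision thresholds and sample size are unchanged.
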